10. MEASUREMENT OF EFFECT

10.1. Although response is not the primary endpoint of this trial, patients with measurable disease will be assessed by standard criteria. In addition to a baseline scan, confirmatory scans will also be obtained. Response and progression will be

evaluated in this study using RANO (radiographic assessment in neuro-oncology) criteria. (<http://neurooncology.ucla.edu/pub/20231676.pdf>)

10.2. Definitions

10.2.1. **Quality of Life (QOL)**: QOL will be assessed using the FACT-Br QOL tool. See Appendix I. QOL scores pre-intervention will be compared to post intervention-QOL score. QOL will also be obtained at the post-treatment visit #2 to assess if termination of intervention decreased QOL score. We understand that there are many variables that can affect QOL during this time other than the intervention.

10.2.2. **Two-year survival (2YS)**: Duration of survival will be defined as the number of months from diagnosis to death due to any cause.

10.2.3. **6-month progression free survival (6moPFS)**: will be defined as the percentage of patients without progression (defined below) at 6 months.

10.2.4. **Ketosis**: Will be defined as serum BHB ≥ 0.5 mM

10.2.5. **Compliance**: Dietary adherence is assessed by review of the daily food diary (Appendix II) serum ketone levels.

10.3. **Methods for Evaluation of Measurable Disease**: All baseline evaluations should be performed as closely as possible to the beginning of treatment. MRI imaging techniques that can be used to determine progression are:

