6.3. Duration of Follow Up

6.3.1. Patients will be followed for toxicity for 14 days after treatment has been discontinued or until progression/death, whichever occurs first

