10.3.5. T1 post-contrast axial and coronal images

10.4. Response Criteria

10.4.1. Evaluation of target lesions will use the Radiographic Assessment in Neuro-oncology (RANO) criteria. See Appendix V will be defined as by RANO criteria.

10.4.1.1. >5 mm increase in maximal diameter, as well as $\geq 25\%$ increase in the sum of the products of the progressing

10.4.1.2. Significant increase in T2/FLAIR non-enhancing lesion compared with baseline (post-chemoradiation) or best response after initiation of therapy, not caused by comorbid events (e.g., radiation therapy, demyelination, ischemic injury, infection, seizures, postoperative changes, or other treatment effects)

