10.4.1.3. Clear progression of non-measurable disease

10.4.1.4. Any new lesion

10.5 Statistics

10.5.1 Ketosis will be defined as serum BHB > 0.05 mM throughout 6-week period of radiation and chemotherapy. We hope to find that in our given sample of 30 patients at least 50% will meet this criteria. We will compute a 95% confidence interval for this rate to estimate the likely range in the target population. A 10% increase in glutamate within the tumor on the post-RT MRI as compared to the pre-RT MRI will be considered evidence that the tumor is using ketones as fuel by the conversion to glutamate.

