APPENDIX V

RANO Criteria for Response Assessment using MRI

From: Wen 2010. **Response**

Complete Response

Criteria

Requires all of the following: complete disappearance of all enhancing measurable and non-measurable disease sustained for at least 4 weeks; no new lesions; stable or improved non-enhancing (T2FLAIR) lesions; patients must be off corticosteroids (or on physiologic replacement doses only); and stable or improved clinically. Note: Patients with non-measurable disease only cannot have a complete response; the best response possible is stable disease.

Partial Response

Requires all of the following: $\geq 50\%$ decrease compared with baseline in the sum of products of perpendicular diameters of all measurable enhancing lesions sustained for at least 4 weeks; no progression of non-measurable disease; no new lesions; stable or improved non-enhancing (T2/FLAIR) lesions on same or lower dose of corticosteroids compared with baseline scan; the corticosteroid dose at the time of the scan evaluation should be no greater than the dose at the time of baseline scan; and stable or improved clinically. Note: Patients with non-measurable disease only cannot have a partial response; the best response possible is stable disease.

Stable Disease

Requires all of the following: does not qualify for complete response, partial response, or progression; stable non-enhancing (T2/FLAIR) lesions on same or lower dose of corticosteroids compared with baseline scan. In the event that the corticosteroid dose was increased for new symptoms and signs without confirmation of disease progression on neuroimaging, and subsequent follow-up imaging show that this increase in corticosteroids was required because of disease progression, the last scan considered to show stable disease will be the scan obtained when the corticosteroid dose was equivalent to the baseline dose.

Progressive Disease

Defined by any of the following: $\geq 25\%$ increase in the sum of the products of maximal perpendicular diameters of enhancing tumor(s) compared to the smaller of pre-SL-701 baseline or best response following initiation of SL-701; New measureable contrast-enhancing lesion(s) defined as lesion(s) that measure at least 1 cm in at least 2 planes; Significant clinical decline not attributable to co-morbid event or change in concurrently administered medication.

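### The 6-month PFS definition names neither death nor a time origin, and the two progression rules it relies on disagree

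*Combined protocol and SAP*

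**What the plan says.** Six-month PFS compared with historical controls is the first secondary objective (1.3.1), and section 9.1 intends to relate the level of ketosis to it. The whole definition is in section 10.2.3: 6-month PFS "will be defined as the percentage of patients without progression (defined below) at 6 months".

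Progression is described in two places. Section 10.1 says that response and progression will be "evaluated in this study using RANO (radiographic assessment in neuro-oncology) criteria" and gives a web link. Section 10.4.1 then lists criteria and refers to Appendix V.

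- **Section 10.4.1.** Item 10.4.1.1 asks for a ">5 mm increase in maximal diameter" together with a rise of at least 25% in the lesion products; its sentence breaks off in the available text. Item 10.4.1.4 adds "Any new lesion".
- **Appendix V.** A 25% rise is enough, measured "compared to the smaller of pre-SL-701 baseline or best response following initiation of SL-701". A new lesion must reach 1 cm in two planes. Significant clinical decline also counts, unless a comorbid event or a medication change explains it.

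Other sections do name death. Section 10.2.2, directly above the PFS definition, reads "Duration of survival will be defined as the number of months from diagnosis to death due to any cause". Section 6.3.1 follows patients for toxicity for 14 days after treatment or "until progression/death, whichever occurs first". Section 3.3 enrols thirty evaluable patients without defining the term. The only statistics paragraph (10.5.1) covers the ketosis rate and tumour glutamate, not PFS.

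**The concern.** A single-arm rate can be set against historical controls only if both sides count the same events from the same starting date. Here the event rule leaves out death, the starting date is missing, and no historical series is named from which either could be inferred.

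The death gap works in one direction. Unless a death without documented progression is counted as an event, the rate goes up, and a larger sample would not remove that. Such deaths are foreseeable: eligibility allows ECOG performance status up to 3 (4.1.4) and requires a life expectancy of only more than three months (4.1.5). Separately, if two pages give different progression rules, the same scan can be an event or not depending on which page the assessor uses.

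**Working it through.** The documents give no 6-month PFS figure, historical rate or event count, so there is no stated number to reproduce. The check compares the text and then sizes each gap.

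**1. Where death is named**

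| Place | Subject | Death named? |
|---|---|---|
| 10.2.2 | Two-year survival | Yes, counted from diagnosis |
| 10.2.3 | 6-month PFS | No, and no starting date |
| 10.4.1.1 to 10.4.1.4 | Progression | No |
| Appendix V | Progression | No, but clinical decline is listed |
| 6.2.6 | End of treatment | Yes |
| 6.3.1 | Toxicity follow-up | Yes |

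The gap is therefore limited to deaths with no recorded progression and no qualifying clinical decline. It includes a death after a decline attributed to a comorbid event, because Appendix V excludes such a decline.

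**2. Size of the death gap.** Let x be the patients alive and progression-free at six months and d the deaths in the gap, with n = 30 (section 3.3). The rate is x/30 if death is an event, (x + d)/30 if it is scored as a success, and x/(30 − d) if it is dropped. Each death scored as a success adds 1/30 = 3.3 points. As an illustration only, assume x = 15 and d = 1 to 3:

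| d | Event | Success | Dropped |
|---|---|---|---|
| 1 | 15/30 = 50.0% | 16/30 = 53.3% | 15/29 = 51.7% |
| 2 | 15/30 = 50.0% | 17/30 = 56.7% | 15/28 = 53.6% |
| 3 | 15/30 = 50.0% | 18/30 = 60.0% | 15/27 = 55.6% |

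The exact (Clopper-Pearson) 95% interval for 15/30 is 31.3% to 68.7%, wide compared with these shifts.

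**3. Time origin.** Six months is 365.25/2 = 182.6 days. The nominal days come from the schema and section 3.2.

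- Diagnosis (Day −28): −28 + 182.6 = Day 155
- Diet start (about Day −7): −7 + 182.6 = Day 176
- Radiation start (Day 0): Day 183

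The landmark can move by 28 days. How far that moves the rate depends on a PFS curve that the documents do not give.

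**4. The two size rules.** For a round lesion of diameter D the product is D². A 25% rise in product is a factor √1.25 = 1.118 in diameter, a gain of 0.118 × D. That gain reaches 5 mm at D = 5/0.118 = 42.4 mm. Below this baseline, a lesion can satisfy the 25% rule without growing by more than 5 mm. Example: growth from 30 to 34 mm is +4 mm, with product (34/30)² − 1 = +28%. This is progression under Appendix V but not under 10.4.1.1. A new lesion smaller than 1 cm splits the other way: it counts under 10.4.1.4 but not under Appendix V's new-lesion criterion.

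**5. Second post-treatment visit.** The schema counts 126 to 154 days from the post-treatment MRI (about Day 70), literally 70 + 126 = Day 196 to 70 + 154 = Day 224. Appendix IV puts the visit two to three months after the first post-treatment visit: Day 126 to 154 with 28-day months (70 + 56, 70 + 84), or about Day 131 to 161 with calendar months (70 + 60.9, 70 + 91.3). The schema's numbers match study days under the 28-day reading, so the two entries need reconciling.

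**The case against.** The strongest reply is that the endpoint is called progression-free survival, that a dead patient does not meet that description, and that section 6.3.1 pairs progression with death. This stands as evidence of intent. A reader might infer that the plan deliberately counts deaths as successes; no section says so, and the documents do not support that reading. What remains is that the operative sentence, followed literally, does not make such a death an event, and the undefined term evaluable leaves room to drop it.

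It is also fair that section 10.1 adopts RANO through a linked paper that was not available here, and that 10.4.1.1 is visibly cut off, perhaps by the PDF reading. The claim about death therefore concerns the protocol's own text.

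Two further inferences are tempting but do not hold.

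- **A baseline contradiction.** Item 10.4.1.2 measures change "compared with baseline (post-chemoradiation) or best response after initiation of therapy", which looks opposed to the SL-701 baseline in Appendix V. But 10.4.1.2 concerns T2/FLAIR non-enhancing lesions, while Appendix V's baseline concerns enhancing tumour. The corresponding enhancing-lesion item, 10.4.1.1, breaks off before any baseline could appear. Only the reference to an agent outside this trial stands.
- **The second post-treatment MRI always precedes six months.** That depends on mixing month lengths. With 28-day months throughout, six months is 168 days, or Day 140 from diagnosis, inside Day 126 to 154. With calendar months, Day 155 lies inside Day 131 to 161.

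Finally, this is a small feasibility study and the endpoint is secondary. That limits the weight of the point but does not answer it.

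**Conclusion.** The point holds for the protocol's text and should be corrected, though it is not critical. The 6-month PFS definition does not provide for death, has no starting date, and relies on two progression rules that can classify the same scan differently.

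The firm figures are 3.3 points for each affected death scored as a success, a 28-day spread between candidate landmarks on nominal schema days, and a divergence of the size rules below a baseline of about 42 mm for round lesions. The number of affected deaths and the 15/30 example are assumptions. The resulting shift is small against the confidence interval, but it always favours the diet.

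No decision rule depends on this endpoint, and the primary ketosis estimate is untouched. What is lost is the historical comparison in objective 1.3.1, which cannot be matched to any series as the plan is written.

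**What to change.** Reword section 10.2.3 along these lines: *the proportion of patients alive and without RANO progression 6 months after [one named origin]; death from any cause before 6 months is an event.* Name the historical series and use its origin and event definition. State the denominator, for example all patients who started the diet, and report an exact 95% confidence interval.

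Reconcile 10.4.1 with Appendix V into one progression definition, settling the >5 mm condition and the minimum size of a new lesion. Replace the SL-701 wording with this trial's own baseline, and complete 10.4.1.1 if the source text is also cut off. Reconcile the timing of the second post-treatment visit between the schema and Appendix IV.

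The cost is a wording amendment, with no new visits or scans. The downside is that the reported 6-month PFS may be slightly less favourable.

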10.3.1. T2-weighted MRI, Fluid-attenuated, inversion-recovery (FLAIR) MRI

10.3.2. Diffusion-weighted imaging (DWI)

10.3.3. T1 pre-contrast MRI

10.3.4. Perfusion including dynamic-contrast-enhanced (DCE) followed by dynamic-susceptibility- contrast (DSC) MRI

10.3.5. T1 post-contrast axial and coronal images

10.4. Response Criteria

10.4.1. Evaluation of target lesions will use the Radiographic Assessment in Neuro-oncology (RANO) criteria. See Appendix V will be defined as by RANO criteria.

10.4.1.1. >5 mm increase in maximal diameter, as well as $\geq 25\%$ increase in the sum of the products of the progressing

10.4.1.2. Significant increase in T2/FLAIR non-enhancing lesion compared with baseline (post-chemoradiation) or best response after initiation of therapy, not caused by comorbid events (e.g., radiation therapy, demyelination, ischemic injury, infection, seizures, postoperative changes, or other treatment effects)

10.4.1.3. Clear progression of non-measurable disease

10.4.1.4. Any new lesion

10.5 Statistics

10.5.1 Ketosis will be defined as serum BHB > 0.05 mM throughout 6-week period of radiation and chemotherapy. We hope to find that in our given sample of 30 patients at least 50% will meet this criteria. We will compute a 95% confidence interval for this rate to estimate the likely range in the target population. A 10% increase in glutamate within the tumor on the post-RT MRI as compared to the pre-RT MRI will be considered evidence that the tumor is using ketones as fuel by the conversion to glutamate.

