1. OBJECTIVES

- 1.1. Hypothesis/Rationale of the Study: Modified Atkins diet (MAD) concurrent with radiation therapy will produce ketosis and improve outcomes in patients with malignant gliomas due to increased sensitivity of the tumors to radiation therapy.
- 1.2. Primary Objectives
 - 1.2.1. Assessment of feasibility of inducing ketosis with MAD concurrent with radiation therapy by measuring serum beta-hydroxybuterate
 - 1.2.2. Assessment of fasting glucose and insulin levels with MAD concurrent with radiation therapy
 - 1.2.3. Assessment of compliance with MAD concurrent with radiation therapy
- 1.3. Secondary Objectives
 - 1.3.1. Assessment of 6-month progression-free survival in patients with high-grade gliomas with MAD concurrent with radiation therapy as compared to historical controls
 - 1.3.2. Safety of MAD concurrent with radiation and chemotherapy therapy
- 1.4. Exploratory Objectives
 - 1.4.1. Assessment of QOL changes with MAD concurrent with radiation therapy
 - 1.4.2. Assessment of cognitive function changes with MAD concurrent with radiation therapy
 - 1.4.3. Assessment of 2-year survival of patients with high-grade primary brain neoplasms with MAD concurrent with radiation therapy as compared to historical controls
 - 1.4.4. Assessment of mitochondrial respiration in peripheral platelets and correlate with cognitive findings

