3. STUDY DESIGN

- 3.1. This is a single arm feasibility study.
- 3.2. Study Diet: Patients will be screened for study eligibility and written informed consent will be obtained prior to enrollment. Patients will meet with the registered dietitian (RD) one to four weeks prior to initiation of concurrent radiation and chemotherapy. At that visit, the RD will provide education on all aspects of MAD including meal planning and daily food diary completion (Appendix II). The diet will begin approximately 7 days prior to the initiation of concurrent radiation and chemotherapy and the patient will continue the study diet until the first post-radiation MRI, a time period of approximately 10 weeks. We will obtain blood to assess serum BHB, fasting insulin and glucose, and other chemistries as well as body weight weekly, according to the standard of care, while on chemotherapy and radiation therapy. Participants will receive weekly phone calls from the RD to address any questions or concerns the patient may have regarding the MAD and daily food diary. A food diary (Appendix II) will be used to assess adherence during the 10-week period. All macronutrient intake from food diaries will be entered by study agent into nutrient analysis software. This macronutrient breakdown will be utilized to identify potential problematic macronutrient intake which may be preventing patient from achieving ketosis. This is available online as well.
 - 3.2.1. Temozolomide and radiation will be given according to the standard protocol described by Stupp et al.ⁱ Patients will receive 75 mg/m² of temozolomide concurrent with radiation therapy at standard dose. The dose of radiation and/or chemotherapy and/or steroid may be modified by the attending physician based on clinical indications.
 - 3.2.2. Correlative platelet mitochondrial studies will be drawn on the pre-treatment visit #2, the post-treatment visit #1 and the post-treatment visit #2. Patients are already having blood drawn at these visits as standard of care. This sample will be transported within 6 hours to the laboratory **[name] at Cincinnati Children's Hospital Medical Center** for assessment of mitochondrial respiration in the platelets.
 - 3.2.3. QOL studies will be done at the pre-treatment visit #2, pre-treatment visit #3, weekly during chemotherapy and radiation, at the post-treatment visit #1 and then at post-treatment visit #2

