 - 3.2.4. Neurocognitive testing will be performed at the pre-treatment visit #2, at the post-treatment visit #1 and then at post-treatment visit #2
- 3.3. **Number of Participants:** Thirty evaluable patients will be enrolled. Because this is a feasibility study, ECOG performance status and MGMT methylation which are both predictors of survival will be recorded but not used for stratification.

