7. DOSING DELAYS / DOSE MODIFICATIONS

- 7.1. If serum ketosis is not obtained (BHB ≥ 0.5 mM), the RD will review the daily food diary (Appendix II) to determine if the calculation of net carbohydrate intake is accurate and to modify the diet to obtain ketosis.
- 7.2. If patient develops Grade 3 or Grade 4 toxicity determined to be related to the diet then patient will be removed off diet. Toxicity can be determined by research coordinator, primary investigator or co-investigator.
- 7.3. If patient has a fasting glucose level >90 mg/dl, it will precipitate an evaluation of dietary intake and/or medical issues (i.e. infection).
- 7.4. If patient is admitted to the hospital while on study/diet, compliance with the diet will be up to the admitting physician and the patient. If the admission is secondary to the diet/protocol, this will be documented as a serious adverse event and the diet will be discontinued to till patient returns to Grade 1 level and then the diet can be resumed. If the patient has a second serious adverse event from the protocol, then the patient will be permanently removed from the diet. Please see section 6.2

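### The statistics section sets the ketosis cut-off at 0.05 mM, one tenth of the protocol's own 0.5 mM, so patients the protocol does not regard as ketotic would count as primary successes

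*Combined protocol and SAP*

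**What the plan says.** Inducing ketosis is the first primary objective (section 1.2.1): "Assessment of feasibility of inducing ketosis with MAD concurrent with radiation therapy by measuring serum beta-hydroxybuterate". Its analysis appears only in section 10.5.1, which gives three things:

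- the responder rule: "Ketosis will be defined as serum BHB > 0.05 mM throughout 6-week period of radiation and chemotherapy";
- the target: "We hope to find that in our given sample of 30 patients at least 50% will meet this criteria";
- the analysis: "We will compute a 95% confidence interval for this rate to estimate the likely range in the target population".

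Two other sections give a different cut-off. Section 10.2.4, under the entry for ketosis, says "Will be defined as serum BHB ≥ 0.5 mM". Section 7.1 says "If serum ketosis is not obtained (BHB ≥ 0.5 mM), the RD will review the daily food diary". BHB is drawn weekly during chemoradiation (section 3.2 and the Appendix IV schedule). Section 3.3 fixes the sample size: "Thirty evaluable patients will be enrolled".

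**The concern.** Sections 10.2.4 and 10.5.1 both claim to define the same word, and they disagree in three respects: the cut-off (0.5 against 0.05 mM), the inequality (≥ against >), and the time rule (none against the whole six weeks). Section 7.1 sides with 10.2.4 on the cut-off. Nothing in the documents suggests that a separate, lower value was meant for the analysis.

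The ketosis rate is the main feasibility result and the only outcome with a stated target. Section 10.5.1 does not call it the primary endpoint, but no other text analyses objective 1.2.1. Analysed as written, the trial could report that the diet induces ketosis in at least half of patients when most of them did not hold the level the protocol itself calls ketosis. If instead the cut-off is quietly changed after BHB values have been seen, the responder rule becomes a post hoc choice.

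**Working it through.** **No figure to reproduce.** The plan gives n = 30 and a 50% target without a null rate, alpha, power or interval width, so the check compares the definitions and works out what follows from them.

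**Inputs.** Analysis cut-off > 0.05 mM throughout (10.5.1); protocol cut-off ≥ 0.5 mM (10.2.4 and 7.1); n = 30 (3.3 and 10.5.1); target 50%, i.e. 15/30 (10.5.1); weekly BHB draws (3.2).

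**Step 1: size of the discrepancy.** 0.5 / 0.05 = 10.

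**Step 2: who is reclassified.** Keep the six-week condition and read it as every weekly draw. A patient's status then depends on the lowest draw:

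| Lowest weekly BHB | At > 0.05 mM (10.5.1) | At ≥ 0.5 mM (10.2.4 value) |
|---|---|---|
| ≤ 0.05 mM | failure | failure |
| above 0.05 and below 0.5 mM | **success** | **failure** |
| ≥ 0.5 mM | success | success |

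Only the middle row changes, and only in one direction. With the time rule held fixed, the 0.05 mM cut-off can never give a lower rate than 0.5 mM. Each patient in the middle row is worth 1/30 = 3.3 percentage points.

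**Step 3: illustration with an assumed split.** Suppose 6 patients are always ≥ 0.5 mM, 10 are always between 0.05 and 0.5 mM, and 14 have at least one draw ≤ 0.05 mM.

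- At > 0.05 mM: (6 + 10)/30 = 53.3%, exact 95% CI 34.3% to 71.7%. Target met.
- At ≥ 0.5 mM: 6/30 = 20.0%, exact 95% CI 7.7% to 38.6%. Target missed, and the interval excludes 50%.

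**Step 4: chance of reaching the target over a range of assumptions.** Let p be the true proportion with every draw ≥ 0.5 mM, and m the share of the remaining patients with every draw above 0.05 mM. The rate under 10.5.1 is q = p + (1 − p)m, and the chance of reaching the target at a true rate r is P(X ≥ 15) = Σ C(30,k) r^k (1 − r)^(30−k), summed over k = 15 to 30. For example, p = 0.30 and m = 0.50 give q = 0.30 + 0.70 × 0.50 = 0.65.

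| p | P(≥ 15/30) at 0.5 mM | m | q | P(≥ 15/30) at 0.05 mM |
|---|---|---|---|---|
| 20% | <0.1% | 25% | 40% | 18% |
| 20% | <0.1% | 50% | 60% | 90% |
| 20% | <0.1% | 75% | 80% | >99.9% |
| 30% | 1.7% | 25% | 47.5% | 46% |
| 30% | 1.7% | 50% | 65% | 97% |
| 30% | 1.7% | 75% | 82.5% | >99.9% |
| 40% | 18% | 25% | 55% | 77% |
| 40% | 18% | 50% | 70% | 99% |
| 40% | 18% | 75% | 85% | >99.9% |

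Both p and m are assumptions; the documents supply neither. The table shows that the cut-off alone can decide whether the target is reached.

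**The case against.** The contradiction itself cannot be disputed, so the case on the other side concerns its weight and its repair.

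- **It is a decimal slip that everyone will read as 0.5.** Probably so, since 0.5 appears in the two other places. But the analysis text as written says 0.05, and the correction should be on record before the rate is computed.
- **The harm is hypothetical.** No document shows that any patient stays between the two values, and the dietitian review in 7.1 works to move such patients upward. This stands as a limit on the size: the inflation is unknown and could be zero.
- **The six-week condition makes 10.5.1 stricter in time.** True. Section 10.2.4 has no time rule, so a patient at ≥ 0.5 mM in most weeks but ≤ 0.05 mM in one fails 10.5.1. Comparing the two sections exactly as printed, the net direction is not fixed. The 53% and 20% figures above apply the six-week condition to both cut-offs. This does not remove the conflict over the cut-off.
- **An every-draw rule at 0.5 mM is demanding.** If each draw independently had a 90% chance of qualifying (an assumption), 0.9^6 = 53% of patients would qualify with six draws and 0.9^7 = 48% with seven. The 50% target therefore needs a second look once the rule is settled. This is a fair point for the fix.
- **There is no test or go/no-go rule, only a hope.** True, and BHB values are collected either way, so no information is lost. The reported rate and its interval still depend entirely on who counts as a success.

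**Conclusion.** The concern holds. Section 10.5.1 is wrong as written: its cut-off is ten times below the value the protocol gives in 10.2.4 and 7.1, and it governs the only stated analysis of primary objective 1.2.1. With the six-week condition kept, the error can only raise the reported rate, by 3.3 points for each patient whose lowest draw lies above 0.05 and below 0.5 mM. In the scenarios examined it is large enough to turn a missed target into a met one. The actual inflation cannot be derived from the documents. The conclusion rests on reading the six-week condition as every weekly draw, and on taking the ketosis rate as the primary endpoint because it is the sole analysis of that objective. It must be corrected before the analysis.

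**What to change.** In section 10.5.1, replace the > 0.05 mM cut-off with ≥ 0.5 mM, the value in 10.2.4 and 7.1, and use it for the responder rate, its 95% confidence interval and the 50% target. In the same edit:

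- state that the six-week condition means every scheduled weekly draw during chemoradiation, and how a missed draw counts;
- have 10.2.4 refer to this rule, so that the endpoint has one cut-off, one inequality and one time rule;
- confirm that 50% is still the intended target under that rule.

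Date the change before the ketosis rate is computed. This alters an endpoint definition only; the diet procedures in section 7 are untouched. The cost is a short amendment and possibly a lower reported rate. No additional patients, visits or blood draws are needed.

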STUDY NUMBER: **UCCI-BRAIN-16-01**

STUDY TITLE: Feasibility Study of Modified Atkins Ketogenic Diet in the Treatment of Newly Diagnosed Malignant Glioma

PRINCIPAL INVESTIGATOR: [name]
Adjunct-Associate Professor of Medicine
Division of Hematology/Oncology
[name]
[name]
[contact]
[contact]
[contact]

CO- INVESTIGATORS

[name], RD, CSO, LD
Clinical RD, Specialist in Oncology Nutrition
University of Cincinnati Cancer Institute
[name]
[name]
[name]
[contact]
[contact]
[contact]

STATISTICIAN:

[name]
Research Associate Professor of Psychiatry
Department of Psychiatry and Behavioral Neuroscience
University of Cincinnati Academic Health Center
[name]
[name]
[contact]
[contact]
[contact]

SUPPORT: UC Brain Tumor Center [name] Endowed Chair Fund

AGENT: Temozolomide

SCHEMA:

1. Diagnosis of High Grade Glioma (-28 days)
2. Pretreatment Visit 1: Meet with Physician and/or Nurse Practitioner (NP) for chemotherapy teaching. (day -28 to day -7)
 - a. Check lipid profile, complete metabolic panel, complete blood count with differential (CBC with diff), and hemoglobin A1C
 - b. Take medical history concerning pancreatitis, recent cholecystectomy or gallbladder dysfunction, diabetes, dairy allergies and/or lactose intolerance, in-born errors of metabolism
 - c. Obtain informed consent
 - d. Obtain tissue from biopsy or resection
3. Pretreatment Visit 2: Meet with Nurse Practitioner for chemotherapy teaching (day -28 to day -7)
 - a. Laboratory Correlatives
 - i. Serum beta-hydroxybutyrate (BHB)
 - ii. Complete metabolic panel, fasting serum glucose and insulin
 - iii. Vital signs, height, body weight, waist circumference
 - iv. Platelet mitochondrial labs
 - v. Neurocognitive testing (See Appendix VI)
 - vi. Quality of Life (FACT-Br) survey (See Appendix I)
 - vii. MRI planning scan
4. Pretreatment Visit 3: Meet with registered RD (RD) for nutritional education concerning carbohydrate restricted diet (Modified Atkins Diet (MAD)) (day -28 to day -7)
 - a. Diet education consultation with RD – 1.5 hours. Distribute week 1 food diary with education concerning completion (Appendix II)
 - b. Confirm above histories and labs
 - c. Random assignment to MAD ketogenic diet with radiation therapy day -7
5. Radiation/Chemotherapy commences (Day 0-Day 42)
 - a. Collect daily food diaries
 - b. Weekly visits with NP/MD
 - i. Serum BHB

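### The only analysis specified for BHB feasibility scores each patient once, all or nothing, so with a 0.5 mM cut-off it cannot tell five of six weeks in ketosis from none

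*Combined protocol and SAP*

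**What the plan says.** Objective 1.2.1 is "Assessment of feasibility of inducing ketosis with MAD concurrent with radiation therapy by measuring serum beta-hydroxybuterate". Section 3.2 provides for weekly BHB during chemoradiation, and the schema and Appendix IV put that period at Day 0 to 42. This gives 6 values per patient, or 7 if both ends are sampled.

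Section 10.5.1 turns the series into one result per patient: BHB must exceed 0.05 mM "throughout 6-week period of radiation and chemotherapy". It hopes that at least half of 30 patients will meet this, and it plans a 95% confidence interval for the rate. It does not say which draws count or how a missed draw is scored. It plans no proportion of weeks, time to ketosis or repeated-measures summary.

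Section 10.2.4 defines ketosis with a different cut-off and no duration: "Will be defined as serum BHB ≥ 0.5 mM". Section 7.1 expects some low readings: "If serum ketosis is not obtained (BHB ≥ 0.5 mM), the RD will review the daily food diary", to check that the "calculation of net carbohydrate intake is accurate and to modify the diet to obtain ketosis".

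BHB has two other stated uses. Section 9.1 will correlate its level with outcome, and sections 9.1 and 10.2.5 use it to judge compliance. Neither has a stated method.

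**The concern.** The protocol manages ketosis week by week but analyses it once per patient. With a 0.5 mM cut-off, a patient who dips in week 1, has the diet adjusted under 7.1 and is in ketosis for the other five weeks is a failure. So is a patient who never reaches ketosis. For a feasibility study these are different findings: the first suggests a workable diet that needs early support, the second a diet that does not work in this setting. A low rate in 10.5.1 could mean either, and the planned analysis would not show which.

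**Working it through.** **What can be reproduced.** No null rate, power or target width is stated, so the choice of 30 cannot be re-derived. At exactly 15/30 the 95% interval is 31.3% to 68.7% (Clopper-Pearson).

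**Does the 7.1 argument hold at both cut-offs?**
- At 0.5 mM, any value that triggers 7.1 is also a failing value in 10.5.1, so later correction cannot restore the patient.
- At the printed > 0.05 mM, a patient at 0.2 mM triggers 7.1 and still passes. Correction could then prevent a later failure, and a patient who never reaches 0.5 mM could pass every week.
- The reduction to one all-or-nothing score is the same at either cut-off. Only its link to 7.1 depends on 0.5 mM.

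**How strict is passing every draw?** The documents give neither the per-draw rate p nor the within-patient correlation ρ. Both are assumed here.
- Independent draws: P(all k) = p^k. With p = 0.85, 0.85^6 = 0.377 and 0.85^7 = 0.321.
- Correlated draws (beta-binomial): a = p(1−ρ)/ρ, b = (1−p)(1−ρ)/ρ, and P(all k) is the product over j = 0 to k−1 of (a+j)/(a+b+j).
- Worked case, ρ = 0.2: a = 3.4, b = 0.6. For k = 6, (3.4/4)(4.4/5)(5.4/6)(6.4/7)(7.4/8)(8.4/9) = 0.531. For k = 7, multiply by 9.4/10 to get 0.499.

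The third column is the binomial probability of at least 15 passes in 30. The last column solves P(all k) = 0.5 for p; under independence this is 0.5^(1/6) = 0.891 and 0.5^(1/7) = 0.906.

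| ρ | Pass all 6 / 7 draws at p = 0.85 | P(at least 15 of 30) | p needed for a 50% pass rate |
|---|---|---|---|
| 0 | 37.7% / 32.1% | 0.12 / 0.03 | 89% / 91% |
| 0.2 | 53.1% / 49.9% | 0.70 / 0.57 | 84% / 85% |
| 0.4 | 63.7% / 61.8% | 0.96 / 0.93 | 78% / 79% |
| 0.6 | 71.9% / 70.8% | above 0.99 | 70% / 71% |

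**Who are the failures?** Take p = 0.80 (also assumed) and 6 draws, under the same model. Among patients scored as failures, 39%, 30% and 21% missed just one week at ρ = 0.3, 0.5 and 0.7, and 3%, 13% and 32% were never in ketosis. So 68% to 97% of failures were in ketosis in at least one week. The rate in 10.5.1 shows none of this.

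**Missed draws.** If each draw has an assumed 5% chance of being missed, independently, 0.95^6 = 73.5% or 0.95^7 = 69.8% of patients have a complete series. At 10% it is 53.1% or 47.8%. The unstated missed-draw rule can therefore move the strict rate considerably.

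**The case against.** The strongest reply is that sustained ketosis is the right target. The objective ties ketosis to the period of radiation, the hypothesis is radiosensitisation, and section 6.1.1 speaks of both reaching and maintaining ketosis. On that view an interrupted course is properly a failure. This stands, and it is why the strict rate should remain the main measure.

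It is also true that 10.5.1 expresses a hope, not a decision rule, and that an investigator could describe the weekly values in a report without any change to the plan. That limits what is at stake. It does not supply a pre-specified summary, with a stated denominator and missed-draw rule, of how often ketosis was achieved.

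Three stronger readings are tempting, and the documents do not support them:
- A reader might infer that correction under 7.1 can never affect the result. On the cut-off printed in 10.5.1 that is not so.
- A reader might infer that most of the BHB data are wasted. The values are collected, and sections 9.1 and 10.2.5 give them other uses, however thinly specified. They are lost only from the feasibility analysis.
- A reader might infer that the weekly proportion would give a more precise answer. It is a different estimand, so its interval width cannot be compared like for like with that of the patient-level rate.

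**Conclusion.** The point holds in a limited form. Section 10.5.1 is the only analysis specified for objective 1.2.1 (the section does not itself use the label primary endpoint). It scores each patient once, and at a 0.5 mM cut-off it cannot separate a patient corrected under 7.1 from one never in ketosis.

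A reader might go on to infer that the trial will probably miss its 50% hope even if patients are in ketosis most weeks. The arithmetic does not support that in general. At an assumed 85% per draw, a miss is likely only near independence. At correlation 0.2 the chance of reaching 15 of 30 is 0.57 to 0.70, and at 0.4 it is 0.93 to 0.96. Repeated draws in one patient are unlikely to be independent.

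The case for change is therefore interpretability: the same strict rate can describe very different diets. This is an inexpensive improvement, not a flaw that undermines the study.

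**What to change.** 1. Reconcile the cut-off in 10.5.1 (> 0.05 mM) with 10.2.4 and 7.1 (≥ 0.5 mM) first, and use one cut-off for both measures below. Otherwise one section would report ketosis at two thresholds.
2. Keep the patient-level rate over the whole 6 weeks, with its 95% confidence interval, as the main measure. Name the weekly draws it covers.
3. Add a supporting measure in the same patients: the proportion of scheduled weekly draws from Day 0 to 42 in ketosis, with a GEE or cluster-robust 95% confidence interval. State who those patients are, because section 3.3 does not define evaluable.
4. Count a missed draw as not in ketosis in both measures, with a sensitivity analysis on observed draws only.
5. Report both measures when judging feasibility.

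The cost is a few sentences in 10.5.1 and one more analysis. No extra visits, blood or patients are needed. The missed-draw rule is conservative and will lower both rates somewhat; the sensitivity analysis shows by how much.
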